Aim 2: Pilot testing the effect of the tailored iHBE on fatigue, pain, affective well-being, resilience and BDNF level among low-income cancer survivors living with co-morbid conditions at completion (12 weeks) and 6 months in comparison to usual care waiting list group.

After adjustment in the protocol based on Aim 1, 50 participants who meet the inclusion criteria will be randomly assigned to a 12-week experimental (preferred physical activities) group or a usual care usual care (waiting list) group. Variables will be measured at baseline, completion (12 weeks) and 6 months.

Hypothesis 2: After controlling for the age, gender, race, and BMI, participants in the experimental group will have a greater decline in fatigue, pain, and a greater increase in AWB, resilience and BDNF level from baseline to program completion and 3 months compared to the usual care group.

Aim 3: Examine the association between the changes in the biomarker (BDNF) in serum and sweat after the 12-weeks from baseline and at 3 months post program completion from baseline iBHE program. Hypothesis 3: the change in the serum BDNF level is positively associated with a change in the sweat BDNF level at the after the 12-weeks from baseline and at 6 months from baseline iBHE program.

Sample and Setting:

The study participants will be recruited from the home health care agencies in Baltimore, Maryland, Johns Hopkins Comprehensive Cancer Center and Johns Hopkins Hospital.

Inclusion criteria are (1) participants diagnosed with solid tumor cancer who have completed cancer treatment at least 6 months; (2) diagnosed with diabetes and/or hypertension for at least a year; (3) aged 21 years or older, (4) have an annual household incomes of below \$30,000 for families of three, (5) the average fatigue level within the past 7 days at the level of 3 or more on the 0 (no fatigue) to 10 (worse fatigue) Likert scale and (6) give informed consent.

Exclusion criteria are those (1) currently undergoing treatment for cancer; (2) have an active infection (e.g., fever, localized redness, swelling, sinus congestion); and/or (3) diagnosed with a psychological disorder (e.g., suicidal or homicidal tendencies, extreme anxiety or depression).

Sample size justification

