Phase 2: With an alpha level of .05, the statistical power of 0.80, and 25 participants per group, we will be able to detect significant differences of moderate to large effect sizes of 0.65 when comparing change across baseline, 3-months, and 6-months between the two groups. With an attrition rate of 12% (22 participants per group), the detectable effect size increases to 0.69. Since this is a pilot study and not powered to detect small to moderate effect sizes, we will pay close attention to the effect size, rather than statistical significance. These effect size estimates will be used to inform future research trials.

Date: November 14, 2018

Principal Investigator: [name]

Application Number: IRB00175781

Randomization: Eligible participants will be randomized in a 1:1 allocation ratio to one of the two treatment arms. The electronic Research Electronic Data Capture (REDCap), a randomization application will be used to randomly assigned the participants to the groups

Data Collection Schedule and Procedures. Upon receiving approval from the Johns Hopkins University Institutional Review Board, the study flyer will be posted and distributed at the home health care agencies in Baltimore, Maryland, Johns Hopkins Comprehensive Cancer Center and Johns Hopkins Hospital.

Recruitment, Informed Consent, and Confidentiality. Recruitment methods for this study include (1) distributing and posting flyers, with a tear-off phone number to speak with the principal investigator (PI) as necessary, posted at the hospital (2) face-to-face recruitment for potential participants during cancer support group meetings; and (3) word-of-mouth. Potential participants will receive a verbal explanation by phone or face to face meeting in terms suited to their comprehension of the purpose, procedures, and potential risks of the study. During the screening for eligibility process, an oncologist will be available for consultation. The oncologist will be notified and consulted for the appropriateness of the exercise for participants who self-report having co-morbidities. The participants and family or legal guardian will have an opportunity to carefully review the consent form and ask questions regarding this study prior to signing. Participants will be encouraged to consult with their primary doctor if any concern or an additional question. Participants will be informed that they may withdraw from the study at any time without prejudice to themselves.

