Exclusion criteria are those (1) currently undergoing treatment for cancer; (2) have an active infection (e.g., fever, localized redness, swelling, sinus congestion); and/or (3) diagnosed with a psychological disorder (e.g., suicidal or homicidal tendencies, extreme anxiety or depression).

6. Drugs/Substances/Devices

None

7. Study Statistics

Phase 2 Data analysis

To test **Hypothesis 2 (Aim 2)** examining the effectiveness of iHBE program on fatigue, pain, well-being, resilience and BDNF levels, generalized estimating equations (GEE) will be used. The models will include time as a within-subject fixed effect (baseline, 3 months, 6 months), group (intervention vs usual care) as a fixed-effect between-subject factor and the group by time interaction. Baseline age, race gender, and BMI will be included as covariates. A significant group by time interaction would signify that the change over time in the outcomes differed for the intervention and usual care groups. GEE was selected because it uses all available data and does not require complete data across time for a participant to be included in the analyses. Correlation will be used to test the relationship between the changes in serum and sweat BDNF levels (**Aim 3**). Change from baseline to 3 months and change from baseline to 6 months will be computed for serum BDNF and separately for sweat BDNF. The correlation between the change scores measured by the different modes will be estimated at each time point

8. Risks: Same as phase 1

9. Benefits: Same as phase 1

10. Payment and Remuneration

Date: November 14, 2018

Principal Investigator: [name]

Application Number: IRB00175781

Phase 2 (Aim 2 and 3) - The participants in both the intervention group and the control group will each receive a total of \$80 (\$20 at the start of the intervention, \$30 at the end of the intervention and \$30 at 6 months)

11. Costs

There will be no cost for participants to participate in this study.

12. Data Safety Monitoring Plan

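### The Aim 3 serum–sweat correlation has no term for randomised group and no stated analysis set, so if the arms are pooled a shared treatment shift in BDNF would inflate it.

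*Combined protocol and SAP*

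**What the plan says.** The Aim 3 analysis is in Phase 2, section 7 (Study Statistics). It reads "Correlation will be used to test the relationship between the changes in serum and sweat BDNF levels", defines change from baseline to 3 months and to 6 months separately for each fluid, and ends: "The correlation between the change scores measured by the different modes will be estimated at each time point". The type of coefficient, a group term, stratification and covariates are not given.

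The same paragraph is more specific for Aim 2. Its GEE model includes time, "group (intervention vs usual care) as a fixed-effect between-subject factor and the group by time interaction", and four baseline covariates. None of this is carried over to Aim 3.

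Two hypotheses in the Phase 2 Specific Aims bear on the point:

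- Hypothesis 3 says that "the change in the serum BDNF level is positively associated with a change in the sweat BDNF level".
- Hypothesis 2 predicts, for the experimental group, "a greater increase in AWB, resilience and BDNF level from baseline to program completion and 3 months compared to the usual care group". It does not say whether BDNF means serum, sweat or both.

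The Aim 3 analysis set is not stated. The Phase 2 payment section, labelled for Aims 2 and 3, says "The participants in both the intervention group and the control group will each receive a total of" the same sum, which suggests that both arms serve Aim 3. The wording of Aim 3 itself ties change to the baseline of the exercise program, which could be read as the iHBE arm alone.

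**The concern.** Randomised group is a possible common cause of both change scores. If the program raises BDNF in serum and in sweat, iHBE participants tend to sit high on both axes and usual-care participants low on both. A single correlation across all of them then contains a between-arm part that says nothing about whether a person whose serum BDNF rises more also shows a larger rise in sweat.

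That person-level question appears to be the reason for Aim 3. The Objectives section motivates the sweat measure by noting that serum testing needs a blood draw and ignores time of day and timing of exercise, and it makes comparison of sweat with serum a secondary goal. The better Hypothesis 2 does in both fluids, the less an unadjusted correlation tells us about that comparison. The sample size section says the pilot will look to effect sizes, to inform later trials. For Aim 3, r is the effect size.

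**Working it through.** **Inputs from the documents.** The sample size section gives "With an alpha level of .05, the statistical power of 0.80, and 25 participants per group", with a detectable effect of 0.65, or 0.69 after 12% attrition (22 per group). Allocation is 1:1. Total N is therefore 50 or 44. No target correlation or power is given for Aim 3.

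**Assumed inputs.** These are the within-arm correlation ρ of the two change scores, and the differences d₁ (serum) and d₂ (sweat) between arms in mean change, in within-arm SDs of change. The Objectives section cites a 25% serum rise, but without an SD it cannot be turned into d, and nothing is cited for sweat. I borrow 0.65 and 0.69 only as a scale the plan itself uses; they are Aim 2 detectable effects, not predicted BDNF shifts.

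**The plan's own figures.** A plain two-sample comparison gives (1.960 + 0.842)·√(2/25) = 0.79 and, at 22 per group, 0.84. Neither matches. Multiplying the variance by (1 + 2×0.5)/3 = 2/3, as for the mean of three visits with correlation 0.5, gives 0.647 and 0.690, which match. The 0.5 is my assumption. These figures concern Aim 2 only.

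**Pooled correlation.** With equal arms and unit within-arm SDs, each pooled variance is 1 + d²/4 and the pooled covariance is ρ + d₁d₂/4, so

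r = (ρ + d₁d₂/4) / √[(1 + d₁²/4)(1 + d₂²/4)].

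*Both fluids shift equally, ρ = 0:*

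- d = 0.65: 0.1056/1.1056 = 0.096
- d = 0.69: 0.1190/1.1190 = 0.106
- d = 1.0: 0.25/1.25 = 0.20

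*Both fluids shift equally, ρ = 0.30, d = 0.65:* (0.30 + 0.1056)/1.1056 = 0.367.

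*Only one fluid shifts:* r = ρ/√(1 + d²/4). The multiplier is 0.951 at d = 0.65 and 0.894 at d = 1.0.

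**Rejection rates.** These come from bivariate-normal simulation with at least 40,000 trials per setting, a nominal 5% level, ρ = 0 and the same shift in both fluids. The plan does not state sidedness; Hypothesis 3 is directional.

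| Shift (assumed) | N | Pooled, two-sided | Pooled, one-sided | Adjusted for group |
|---|---|---|---|---|
| 0.65 SD | 50 | 10% | 16% | 5% |
| 0.65 SD | 44 | 9.5% | 15% | 5% |
| 0.69 SD | 44 | 10% | 17% | 5% |
| 1.0 SD | 50 | 29% | – | 5% |
| 1.0 SD | 44 | 26% | – | 5% |

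If only one fluid shifts, by 0.65 SD, with ρ = 0.4 and N = 50, pooled power is 0.79 against 0.83 with adjustment.

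**Cost of adjustment.** The r detectable with 80% power, two-sided 5%, by Fisher's z is tanh[2.802/√(N − 3)], or tanh[2.802/√(N − 4)] for the partial correlation.

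- N = 50: 0.387 pooled, 0.391 adjusted
- N = 44: 0.412 pooled, 0.416 adjusted
- iHBE arm alone: 0.535 (n = 25) or 0.567 (n = 22)

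**The case against.** The strongest reply is that the target is not stated. Hypothesis 3 claims that the two changes are positively associated. If exercise raises both fluids, that is true as a statement about all participants, and the pooled correlation estimates it properly. The 10% is an error rate only if the within-arm association is what is wanted. This stands, and it is why the pooled value should be kept beside the adjusted one. It does not rescue the pooled value as the only estimate, since it cannot separate person-level tracking from a shared response.

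Second, pooling is inferred. A reader might take it as settled that the plan pools the arms; the documents do not say so. An analysis of the iHBE arm alone would have no such artefact, but would use 22–25 people.

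Third, the distortion at 0.65 SD is small: an r of 0.10 would not persuade anyone that sweat tracks serum, and this is a pilot that puts effect size ahead of significance. That also stands, and it limits the weight of the point.

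A reader might also infer that pooling could hide a real relation. Opposite shifts of 0.65 SD would do so: with ρ = 0.4 and N = 44, power would be about 41% pooled against 77% adjusted. But that needs BDNF change to be higher in one fluid and lower in the other under iHBE, and Hypothesis 2 predicts only a greater increase. If one fluid simply fails to respond, r is diluted by about 5% at 0.65 SD.

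**Conclusion.** The point holds as an upward bias under stated conditions: the arms are pooled, iHBE shifts both fluids upward, and person-level tracking is the target. Its size depends wholly on an unknown shift. It is modest at 0.65–0.69 SD (spurious r about 0.10, two-sided rejection roughly doubled) and material at 1.0 SD (r = 0.20, rejection 26–29%). The documents give no BDNF SD from which to say which is nearer. They do not support a claim that the predicted effect would mask a true correlation, or that the Aim 3 result would be invalid. It is worth correcting because Aim 3 is meant to inform later work and the correction is almost free.

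The 6-month estimate carries a further uncertainty. The Phase 2 description of the usual care group places its access to the program after the study ends, while the Phase 2 data collection procedures place it after the 12-week program. What the arm difference means at 6 months is undefined until these are reconciled.

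**What to change.** In Phase 2, section 7, state that Aim 3 uses both arms. Name the main estimate as the partial correlation of serum and sweat BDNF change adjusted for randomised group, with a 95% CI at 3 months and at 6 months. Report the unadjusted pooled correlation beside it, and say that it also includes any shared treatment response. Show scatterplots by arm, because a single adjusted value assumes a similar relation in the two arms.

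Reconcile the two statements on when the waiting-list group receives the program, so that the 6-month estimate can be read by arm.

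The cost is a few sentences of analysis text and one degree of freedom. No new data are needed, and the detectable r rises by only about 0.004. Restricting the analysis to the iHBE arm would also remove the artefact, but would raise the detectable r to about 0.54–0.57.
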